1.4 Preliminary Data

Behavioral Interventions to Address Homework Problems in Adolescents with ADHD. [name] published the findings from a large RCT comparing two behavioral interventions to address the homework problems of adolescents with ADHD to a waitlist control ([name] et al., 2018). One of the interventions, the Homework, Organization, and Planning Skills (HOPS) intervention teaches time-management and organizational skills but like most existing ADHD interventions, does not address focus or efficiency of work completion. The other intervention, Completing Homework by Improving Efficiency and Focus (CHIEF), was specifically designed to improve concentration during homework and studying. In this intervention, a clinician defines on-task behavior and provides frequent and consistent monitoring and rewards using a point system for 20 minutes 2x per week for one academic semester while participants complete homework and study for tests. The intervention was administered individually in a quiet room to reduce distractions. Essentially, the counselor implementing CHIEF is doing what our team proposes to automate.

Adolescents with ADHD in the CHIEF intervention ($N=111$) demonstrated large (d 's range from .9 to 1.10) effect size improvements on parent ratings of homework problems in comparison to the waitlist and significant improvements in the percentage of homework assignments turned-in (M increasing from 69% of assignments to 86% of assignments). This study demonstrates the remarkable potential of VR to significantly improve concentration and academic task completion in emerging adults with ADHD. The VR treatment would be much less time and resource intensive than having a counselor implement the behavioral principles and could individually optimize the delivery of contingency management and ensure a distraction free environment.

FlowLight to Reduce Worker Disruptions. Breaks in concentration lead to significantly reduced worker productivity and creativity. Research suggests that on average if a worker is interrupted at a time of peak performance, it takes up to 20 minutes for them to get back to operating peak performance. Corporations have been working to address this for years, largely through physical barriers such as closed doors or headphones. However, these strategies are not possible to implement in open floor office environments which are the predominant set-up in many office buildings (i.e., cubicles). [name] team developed the FlowLight, that combines a traffic-light like LED with an automatic interruptibility measure based on computer interaction data. The team developed and implemented multiple computer algorithms to accomplish this. The base algorithm is called FlowTracker, which sums up the computer interaction in the past three minutes according to heuristic weights assigned to each type of event. While the FlowTracker is effective, it may be too sensitive to certain input. For instance, a twenty second burst of typing. Therefore, the team developed a Smoothing algorithm which evaluates whether users were active in each of the last three minutes and exceeded a threshold of 100 combined mouse clicks and key presses in the recent past (between 4 and 7 minutes ago). Finally, the team combined the FlowTracker algorithm with the Smoothing algorithm to achieve the advantages of both approaches. This algorithm is similar to the Smoothing method but instead of using a static threshold, it utilizes the FlowTracker algorithm to determine above threshold values.

In a large longitudinal study with 449 participants from 12 countries (Zuger et al., 2019), the team found that FlowLight reduced the interruptions of participants by 46%, increased their awareness on the potential disruptiveness of interruptions, and most participants never stopped using it. Further, 58.5% of participants reported being more productive and that FlowLight increased motivation to persist with tasks.

Virtual Reality Settings to Foster Flow. [name] and colleagues have also published on the impact of VR to foster worker productivity (Ruvimova et al., 2020). These studies included four different conditions, to specifically isolate the impact of a calming beach as a VR environment. Notably, the virtual beach environment was equivalent to a closed office environment in fostering attention and task completion. It is important to note that this version did not incorporate FlowLight, but simply tested the impact of the distraction free beach environment. Accordingly, the VR environment without FlowLight will also serve as one of the conditions in the proposed study, to identify what aspects of VR are most important for individuals with ADHD.

1.5 Sample Size Justification

PHASE 1: Refine objective data capture techniques. 30 participants completing 10 sessions will allow the team to implement and refine the keyboard and mouse click algorithms needed to ensure that we are tracking attention accurately. Since the goal is to refine the algorithms, no control group is needed.

PHASE 2: Develop and refine contingency management algorithms. 30 participants completing 10 sessions will allow for proper testing of the addition of the FlowLight icon (a stoplight) and box showing points earned within the VR environment. The goal is to understand how and when participants like to receive feedback about their on-task behavior and attention. A secondary goal is to understand how best to motivate participants to stay on-task and to complete work efficiently (e.g, a points system). 10 sessions with 30 participants are sufficient for this along with the focus group, and no control group is needed.

PHASE 3: Pilot test and evaluate impact on target mechanisms. 45 participants randomized to 1 of 3 groups will inform the feasibility and usability of the system tested and refined in phases 1 and 2. Though outcome measures will be collected, power analyses are not required due to the pilot status of the trial. The goal of phase 3 is to calculate effect sizes rather than to run statistical tests to begin to understand the magnitude of effects.

PHASE 4: Conduct a parallel group randomized trial. 252 participants randomized to 1 of 3 groups will allow for appropriate comparison across groups. Power calculations were run to determine this sample size. Power calculations are based upon $N = 84$ participants in each condition, for a total sample of 252 college students with ADHD. [name] prior intervention studies focused on improving attention produced effect sizes ranging from .6 to 1.12 comparing treatment to waitlist control. For the purposes of these power analyses, we use an effect size of .8 as the expected effect between the VR environment + contingency management group and passthrough control. This effect is also consistent with meta-analyses of behavioral contingency management interventions. Differences between active intervention conditions in our recent trial ranged between .4 to .6. Accordingly, between group effects (i.e., VR environment only to VR passthrough and to VR environment + contingency management) for the current study were estimated at $d = .4$.

1.6 Study Variables

A. Independent Variables, Interventions, or Predictor Variables

The randomized trial will consist of 3 groups.

1) VR passthrough – participant wears headset but sees through to normal environment and laptop

- 2) VR environment only – participant wears headset and interacts with VR environment
- 3) VR environment + contingency management – participant wears headset and interacts with VR environment while receiving contingency management (real-time feedback on performance through FlowLight icon)

B. Dependent Variables or Outcome Measures

On-task behavior will be measured within the VR environment using keyboard and mouse clicks and FlowLight level.

Attention and concentration will be measured by participant survey report.

Homework motivation will be measured by participant survey report.

Homework effort will be measured by participant survey report.

1.7 Drugs/Devices/Biologics

A. Schedule and Administration

N/A

B. Drug/Device Accountability and Storage Methods

The virtual reality headset is not considered a device under evaluation for the purposes of this study. The FlowLight software, under investigation in the present study, is being used on a VR headset. Risks have been outlined in section 4.7 and the consents. Documentation on the use of the device has been included in the eIRB.

1.8 Specimen Collection

A. Primary Specimen Collection

- Types of Specimens: N/A
- Annotation: N/A
- Transport: N/A
- Processing: N/A
- Storage: N/A
- Disposition: N/A

B. Secondary Specimen Collection

- Types of Specimens: N/A
- Annotation: N/A
- Transport: N/A
- Storage: N/A
- Disposition: N/A

1.9 Data Collection

A. Primary Data Collection

- Location: Assessments (initial evaluation, outcome visit) and focus groups will be completed via HIPAA-compliant videoconference (e.g., Zoom) with the Rutgers study staff. Electronic questionnaires will be sent directly via secure web-based survey sites (e.g., REDCap). Intervention visits will be completed at participants' homes or the LSU/Rutgers library.
- Process of Data Collection: Diagnostic assessments and intervention sessions will be completed by graduate students enrolled in masters or doctoral psychology programs, post-baccalaureate research assistants who have received specialized training, or post-doctoral

fellows. The VR intervention will be supervised by [name] and the diagnostic assessments will be supervised by [name].

- **Timing and Frequency:** Phases will occur in chronological order, with one completing before the next begins. See sections 1.3 C and 1.10 for more information on timing.
- **Procedures for Audio/Visual Recording:** Audio of the focus groups in Phase 2 will be recorded. No other audio/visual data are being collected.
- **Study Instruments:**
 - PUBLISHED
 - SCID-V RV (First et al., 2015)
 - Service Utilization for College Students (Anastopoulos et al., 2018)
 - BAARS-Self (Barkley, 2011a)
 - ADHD Rating Scale – Parent (childhood; DuPaul et al., 2016)
 - Adult Concentration Index (ACI; Fredrick et al., 2021)
 - Homework Motivation Index (Martin, 2001)
 - Homework Effort Index (Trautwein et al., 2006)
 - RCADS (Ebetsutani et al., 2010)
 - Columbia Suicide Severity Index (Posner et al., 2011)
 - BDEFS (Barkley et al., 2011b)
 - BAI-2 (Steer et al., 1997)
 - ADHD Impact Module-Adult (AIM-A; HealthAct, 2007)
 - Systems Usability Scale (Brooke, 1996)
 - GAD-7 (Spitzer et al., 2006)
 - PHQ-9 (Kroenke et al., 2001)
 - BFIS (Barkeley, 2011c)
 - UNPUBLISHED
 - Demographic and Background
 - Current Day Medication Adherence
 - Academic Record (GPA & Percent of Assignments Completed)
 - Reading Comprehension Standardized Assessment
 - Parent Contact Form
 - Subject Contact Form
 - Pre-screening questions
 - WHODAS (Required by NIMH/NDA)
 - DSM-5 Level 1 Cross-Cutting Symptom Measure (Required by NIMH/NDA)

- **Ethnographic Studies, Interviews, Or Observation:** N/A
- **Subject Identifiers:** The kinds of personal identifiers obtained include: names, dates, postal addresses, phone numbers, IP addresses, and email addresses. Person identifiers will be kept electronically in a password protected document on servers or computers that can only be accessed by the study staff. These identifiers will be retained indefinitely if the subject has given consent to be contacted for future research; if the subject does not consent to future contact, identifiers will be discarded when the current IRB protocol expires.
- De-identified data are stored on both the approved secure server (only available to staff) and stored in a password protected shared drive. The shared drive will only be accessible to study staff and approved investigators. All data located on the drive is password protected. For example, participant inclusion/exclusion evaluation reports require a password to open. Only the study coordinator and MPI ([name]) who prepare the reports have access to the password. In addition, staffs' hard drives are encrypted using encryption software. Encryption

software provides a comprehensive Data Protection Platform to control, manage and protect laptops, desktops and self-encrypting drives.

- Precautions used to maintain the confidentiality of identifiable information: Standard practices are used to protect participant confidentiality and personal health information, including removing identifiers from all data collected, using only numbers to identify participant data, and keeping all data files when not in use in a locked filing cabinet behind a locked office. No names or other identifiers are used in computerized data files. REDCap, the survey tool that will be utilized for this project, has many security measures in place to prevent against inappropriate release of survey data and information. REDCap will be used to contact participants via email, collect survey responses, and record survey completion. To provide an additional layer of protection to participants, the collection of direct identifiers will be assessed separately from the general survey(s). The portable laptops that the research assistants use are only for transmitting data. The REDCap database is password protected. The laptops have no data stored on them, except the temporary file while the browser is open. All REDCap transmissions (to and from) are encrypted.

B. Secondary Data Collection

- Type of Records: N/A
- Location: N/A
- Inclusion/Exclusion: N/A
- Data Abstraction Form(s): N/A

1.10 Timetable/Schedule of Events

	Sep	Oct	Nov	Jan	March	April	May	Summer Semester
Year 1 R61	Project 1 Recruitment (N=30) Inclusion/exclusion evaluations			Project 1 Intervention Sessions				Analysis and refinement of algorithms and VR protocol
				Project 2 Recruitment (N=30) Inclusion/exclusion evaluations				
Year 2 R61	Project 2 Intervention Sessions Project 3 Recruitment (N=45)			Project 3 Intervention Sessions				Analysis and refinement and evaluation of Go/No-Go
Year 3 R33	RCT Cohort 1 Recruitment (N = 63)			RCT Cohort 2 Recruitment (N=63)				Analysis and dissemination
Year 4 R33	Cohort 2 Intervention RCT Cohort 3 Recruitment (N = 63)			Cohort 3 Intervention Sessions RCT Cohort 4 Recruitment (N=63)				Analysis and dissemination
Year 5 R33	Cohort 4 Intervention Sessions			Analysis and publication				

Note: Total sample = 252; 4 cohorts of 63 participants each; intervention period for each cohort allows for 1 month of cushion for missed and make-up sessions. December is not shown as no activities occur over winter break although the study team can recruit and provide intervention for the first 1.5 weeks in December.
								

2.3 Other Resources

In the event that a subject finds the assessments and/or intervention mildly anxiety provoking, research staff members will express empathy and appropriate encouragement and reassurance. Risk of emotional distress will be minimized through effective rapport building and interactions with the subjects. A small percentage of subjects might initially feel disoriented or dizzy in the VR environment. Most subjects adjust quickly after taking a break or working in small chunks of time. Should discomfort become sufficient to pose distress for the subject, the research staff member will discuss these reactions to determine whether the subject wishes to continue completing the research procedures.

*Some of the questionnaires and interviews have items that ask about suicidality, and it is possible that subjects will endorse items pertaining to threat to self. These questionnaires are reviewed at their baseline assessment visit. If any items that endorsed suicidality or threat to self were checked by subjects, then the study staff will consult with the PI ([name], who is a licensed clinical psychologist) to complete a risk assessment to determine appropriate actions based on level of risk (e.g., presence of a plan, desire to act on the plan, and access to means to carry out the plan). (see 4.7E for protocol for steps following risk assessment).

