Participants who take psychotropic medications will be asked to remain consistent on the seven days of the trial (i.e., choose to take or not take medications each day that the VR headset is used). The general course of such medication involves such decisions daily, so participants will have received medical consultation from their prescribing physician outside of the context of the study. Participants who have questions about stopping medication will not be advised by the study staff. They will be encouraged to discuss with their prescribing physician. While participating in the VR intervention, they will be wearing a VR headset while completing homework and studying on a laptop. 40 minutes of each session are devoted to work completion. Participants may be offered to complete all 40 minutes at once or to take a 10-minute break. If a session does not meet a 45-minute threshold, the participant will be scheduled to repeat the session.

Initial evaluation: Participants in each phase will complete an initial diagnostic evaluation to confirm eligibility and collect baseline data. The first half of the evaluation will be done via electronic surveys hosted by Rutgers. Subjects will provide contact, demographic, and background information. To measure current symptoms of ADHD and inform diagnosis, they will complete the Barkley Adult ADHD Rating Scale (BAARS-Self). To capture potential risk factors for use of the VR system, prescreening questions will ask about related medical history. To evaluate other services and treatments participants may be receiving, they will complete the Service Utilization for College Student's Questionnaire. To obtain a baseline of treatment targets/mechanisms, participants will complete the Adult Concentration Index, Homework Motivation, and Homework Effort/Efficiency ratings. To measure potential treatment moderators and outcomes, subjects will complete the GAD-7 and PHQ-9, Columbia Suicide Severity Index (CSSI), BDEFS, BFIS, and surveys on Academic Record (self-report only; and GPA & Percentage

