of Assignments Completed). Due to NIMH/NDA data-requirements, in phase 4 of the trial, both the DSM-5 Level 1 Cross-Cutting Symptom Measure and WHODAS (World Health Organization Disability Assessment Schedule) are included. If the participant is eligible based on results of the survey data (see inclusion criteria), they will be invited to schedule an assessment interview over videoconferencing with Rutgers study staff. To measure current symptoms of ADHD and common comorbid disorders (e.g., anxiety and depression) and confirm diagnosis, a study staff member will administer the SCID-V RV.

PHASE 1: Refine objective data capture techniques.

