4.0 Subject Considerations

4.1 Subject Selection and Enrollment Considerations

A. Method to Identify Potential Subjects

Recruitment will be performed at Rutgers and Louisiana State University. The study staff will work with university organizations that have access to the student body in various ways (e.g., listservs, counseling services).

B. Recruitment Details

Recruitment information will be disseminated by organizations which support students with ADHD including university counseling services, disability services, and student health services. This will be done flyers posted in physical spaces on campus and electronic spaces such as the counseling services website. Recruitment information will also be distributed more broadly to students via email to reach students who are not already diagnosed with ADHD and physical flyers in general campus spaces.

C. Subject Screening

Interested students will be directed to a secure website platform and are provided information about the study. If they proceed and sign informed consent, they will complete a measure assessing current DSM ADHD symptoms (BAARS) and prescreening questions about medical history related to use of the VR system. If they endorse at least 5 ADHD symptoms of inattention, they will move forward. If they indicate sensitivity to flashing lights, neurological/vestibular issues, or an implanted medical device, they will not move forward. These questions ensure that students with below threshold ADHD symptoms do not complete all the study measures. If students meet criteria on the ADHD symptom screen and prescreening questions, they proceed to complete the remaining study measures. The last page of the online survey provides participants slots to sign-up for a time to be administered the diagnostic interview virtually. If they do not meet criteria on the BAARS, they will be forwarded to a page informing them that they are not eligible for the study. If the participant completes the surveys and interview and are found not eligible, they will be informed via email.

▪ Inclusion Criteria

- Is assessed to have 5 or more symptoms of inattention on the BAARS.
- Is assessed to have 6 or more symptoms of inattention on the BAARS childhood.
- Meets DSM-5 criteria for ADHD
 - participant endorses at least 6 symptoms in the ADHD inattention domain as present and impairing during participant's childhood

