 - participant endorses a total of at least 5 symptoms in the ADHD inattention domain as currently present and impairing
 - anxiety and depression is also evaluated to determine if ADHD is primary and whether comorbid conditions are present.
- Is between the ages of 18 and 25
- Is enrolled full-time as a student at LSU or Rutgers.
- Is assessed to have more than 3 symptoms labeled often or very often on the Adult Concentration Index (ACI)

▪ Exclusion Criteria

- Diagnosis of autism spectrum disorders, bipolar disorder, obsessive-compulsive disorder, active substance abuse, or other psychiatric conditions
- History of seizures or clinically significant migraines
- Has an implanted medical device
- Neurological or vestibular issues which affect balance or gait

D. Privacy Protections

All electronic assessment data, initial assessment for eligibility, are hosted on university-approved secure servers (e.g., REDCap); access to the completed forms is only available to study team members via their private Rutgers log-ins.

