4.4 Consent Procedures

A. Consent Process

- **Location of Consent Process**

Initial consent will take place online without direct contact with the study staff, though the consent includes information to contact the study team should they have questions about the consent.

▪ **Ongoing Consent**

Participants will be encouraged to keep a copy of their consent form, which will include contact information for the lab in case they have any questions or would like to reconsider participating in the study at any time during the data collection period.

Upon initial direct contact with the study team (i.e., during the virtual administration of the SCID interview), participants will be reminded of the details of the consent and asked if they have questions. The study staff will answer all questions before moving forward with the study procedures.

▪ **Individual Roles for Researchers Involved in Consent**

Members of the study staff conduct informed consent.

▪ **Consent Discussion Duration**

There is no set amount of time allocated for consent discussion. The study team acknowledges that all potential subjects may require different amounts of time to process and ask questions about the information being provided.

▪ **Coercion or Undue Influence**

To protect against coercion or undue influence, the following points are written in the consent/assent documents:

1. Emphasis participation in the study is strictly voluntary and that the participant can choose to withdraw their participation from the study at any time.
2. It will further be emphasized that any decision to withdraw will not affect the adult's ability to make use of clinical services at Rutgers or LSU and will not impact any current or future relations with Rutgers or LSU.
3. Description of study procedures and treatments will be provided, and questions from the adults will be encouraged.
4. The participants will be made aware that the alternative to participating in the study is to not participate.

▪ **Subject Understanding**

Study staff will be trained to review all aspects of the consent form with the participant and to obtain verbal indication from participant that they understand the material. As part of the procedure, study staff will verbally ask questions confirming comprehension of consent at the initial direct contact with the participant (i.e., at the evaluation interview).

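### Suicidality items answered online at baseline are set for review at the later visit, with no deadline from submission and no clear review for subjects who never have that visit

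*Combined protocol and SAP*

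**What the plan says.** The baseline evaluation has two parts. Section 1.3 A (Initial evaluation) states: "The first half of the evaluation will be done via electronic surveys hosted by Rutgers". The Columbia is in that electronic part. Section 1.3 B lists it at the initial evaluation in all four phases, and in Phases 3 and 4 at no later point.

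No staff member is present at this stage. Section 4.4 A says: "Initial consent will take place online without direct contact with the study staff", and it names the diagnostic (SCID) interview as the first direct contact.

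The route to that interview is described in two ways. Section 4.1 C says: "If students meet criteria on the ADHD symptom screen and prescreening questions, they proceed to complete the remaining study measures", and then: "The last page of the online survey provides participants slots to sign-up for a time to be administered the diagnostic interview virtually". Section 1.3 A makes the interview conditional: "If the participant is eligible based on results of the survey data (see inclusion criteria), they will be invited to schedule an assessment interview".

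Section 2.3 sets the review point for questionnaires with suicidality items: "These questionnaires are reviewed at their baseline assessment visit". Endorsement then leads to consultation with the PI and a risk assessment. Section 4.7 D gives the detailed steps. Its procedures name two settings: a report made in an assessment visit and a report made during the intervention.

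**The concern.** A subject can endorse a suicidality item alone at a computer, and the rule as written places the reading of that answer at an appointment on a later, unspecified date. The same statement made to a staff member during a visit would bring a risk assessment before that visit is over. If the appointment never happens, the rule has no point at which it operates.

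Everyone who consents counts as a subject (section 4.3 A), so the duty of care does not depend on eligibility or attendance. In Phases 3 and 4 the baseline survey is also the only listed Columbia collection, so its timing matters more there. What is at stake is subject safety.

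**Working it through.** No power, error rate or event count bears on this point. The check sets the relevant sections side by side and then does simple subtraction on the planned numbers.

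**1. Where each response time starts**
- Section 2.3: review at the baseline visit. No time from survey submission is given.
- Section 4.7 D, risk assessment: before the end of the visit in which the report is made. It starts at the visit.
- Section 4.7 D, psychologist meeting within 24 hours: applies when staff have contacted the on-call psychologist and that person cannot join at once. It starts from staff contact.
- Section 4.7 D, safety check within 72 hours: counted from the risk assessment.
- Section 4.7 D, automatic review of anyone endorsing a suicidality item at every timepoint: no hours or days, no action for a person without a visit, and aimed at detecting increases.
- Section 1.3 C: about 1 week for the whole initial evaluation. This is an approximate duration of involvement, not a review limit.
- Section 6.3: the data and safety monitoring plan is marked not applicable, so it supplies no further rule.

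None of these starts when the survey is submitted.

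**2. Who can complete the items and have no visit**
- Students who fail the ADHD symptom screen or the medical prescreen stop before these items (section 4.1 C). They are not affected.
- Subjects who pass both screens go on to the full battery. Under section 1.3 A, those who then miss another survey criterion, such as the threshold of more than 3 symptoms on the Adult Concentration Index in section 4.1 C, are not invited to interview.
- Others may be offered slots and not book, or book and not attend.

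The inclusion and exclusion criteria do not use the Columbia. An eligibility check on the survey data therefore gives no stated reason to read it.

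**3. Planned numbers (section 4.3 A; randomised numbers from section 1.3 A)**

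Consents minus maximum completers:
- Phase 1: 60 − 30 = 30
- Phase 2: 60 − 30 = 30
- Phase 3: 90 − 45 = 45
- Phase 4: 400 − 252 = 148
- All phases: 610 − 357 = 253

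Subjects who wait between survey and interview include every planned completer: 252 in Phase 4, and 30 + 30 + 45 + 252 = 357 overall. Phases 1 and 2 are not randomised, so the randomised total is 45 + 252 = 297.

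Subjects with no visit: if all 252 Phase 4 places are filled, the count lies between 0 and 148. The same subtraction gives 0 to 253 across phases. These are bounds, not estimates. The excess includes prescreen failures, who never see the items, and subjects who attend and are then found ineligible. No booking, attendance or endorsement rate is given, so the range cannot be narrowed.

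**4. Outcome assessment in Phases 1 and 2**

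The Columbia is repeated there. Section 1.3 A sends Phase 1 subjects a REDCap link and says Rutgers staff perform the assessments in both phases using REDCap. Section 1.9 A describes an outcome visit by videoconference with staff, and also questionnaires sent by web survey. Whether staff are present when the items are answered is unclear.

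**The case against.** The strongest reply is that the protocol already covers this. The lead-in to the procedures in section 4.7 D is general and applies whenever such thoughts are reported. The electronic survey is itself half of the evaluation, so an endorsed survey item could count as a report. The automatic review of endorsers has no attendance condition. Survey data are looked at for eligibility before the invitation, so staff may open the record early. Section 2.3 says the questionnaires are reviewed at the visit; it does not say only then. Subjects who proceed are also seen at the diagnostic interview, asked about their well-being before each session (section 4.7 A, Risk 2) and covered by in-session risk assessment. Section 4.7 D expects such reports to be infrequent.

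Much of this stands. A reader might infer that endorsed answers go unread or without a response; the documents do not support that. What remains is narrower: none of these texts sets a deadline from submission or an action for someone who has no visit. Rarity does not remove the need for a rule, since the protocol sets detailed steps for in-visit reports that it also expects to be rare.

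A reader might also take 148 or 253 as the number left uncovered. The documents do not support that either. Sections 1.3 A (Phase 4) and 4.3 A explain the surplus of consents by ineligibility and do not mention non-attendance. It would likewise go too far to say that the same gap is established for the Phase 1 and 2 outcome assessment, because the mode of that assessment is unclear.

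The consent pages and short parts of the text around section 2.3 were not available. Crisis resources may already be shown on screen.

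**Conclusion.** The point holds for the baseline evaluation in all phases. Followed as written, the plan lets an endorsed suicidality item wait for the appointment, and it gives no clear review for battery completers who are not invited, do not book or do not attend.

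The length of the wait is not stated. It applies to all 357 planned completers, 252 of them in Phase 4, but matters only for those who endorse an item, and that number is unknown. The count without any visit cannot be sized beyond the bounds shown. For the Phase 1 and 2 outcome assessment the point is conditional: it applies only if the items are answered online without staff.

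This rests on reading section 2.3 as the operating rule, and on no unseen text setting a review time from submission. It is a safety gap that is cheap to close, with no effect on the trial's estimates.

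**What to change.** Amend sections 2.3 and 4.7 D as follows:
- Existing trained staff check new baseline survey submissions for endorsed suicidality items, on submission or daily.
- An endorsed item leads to review and an outreach attempt within a stated time, for example by the next business day, through the on-call psychologist already named in section 4.7 D.
- This applies whatever the subject's eligibility, invitation or booking status.
- Crisis resources appear on screen when an item is endorsed, if this is not already done.
- The review at the baseline visit stays as a second check.
- The Phase 1 and 2 outcome assessment follows the same rule if its items are answered online without staff.

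In the same edit, correct the reference in section 2.3, which points to 4.7 E for steps that sit under 4.7 D.

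The cost is some extra staff checking and on-call time, and outreach to people who will not be enrolled. The REDCap features listed in section 6.2 do not name alerts, so an automatic flag is an assumption; a daily manual check would serve. The next-business-day limit is a suggestion, as the documents give no standard for it.
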